11. SAFETY DEFINITIONS, REPORTING, AND MONITORING

11.1. Overview

This section defines the types of safety data that will be collected under this protocol and outlines the procedures for appropriately collecting, grading, recording, and reporting those data. AEs that are classified as serious according to the definition of health authorities must be reported promptly (per **Section 11.7**) to the Sponsor. Appropriate notifications will also be made to site principal investigators (PIs), Institutional Review Boards (IRBs), and health authorities, as needed.

Information in this section complies with ICH Guideline E2A: Clinical Safety Data Management: Definitions and Standards for Expedited Reporting, ICH Guideline E-6: Guideline for Good Clinical Practice (GCP), and 21CFR Parts 312 and 320, and applies the standards set forth in the National Cancer Institute (NCI), Common Terminology Criteria for Adverse Events (CTCAE), Version 5.0.

11.2. Definitions

11.2.1. Adverse Event

Any untoward or unfavorable medical occurrence associated with the use of an intervention in humans, whether or not considered related to the intervention (see 21 CFR 312.32(a)). An AE can be any unfavorable and unintended sign, symptom, or disease temporally associated with the use of a drug, and does not imply any judgment about causality. An AE also includes any worsening (i.e. any clinically significant change in frequency and/or intensity) of a pre-existing condition that is temporally associated with the use of the study drug.

All symptoms or events that occur within two hours and that are expected according to the Investigator's Brochure (milk OIT), package insert (dupilumab), or protocol and related to administration of study drug or oral food challenge will be recorded as a dosing reaction, not an AE; however, episodes in response to home dosing that are Grade 3 or higher per CTCAE V5.0 criteria or that are classified as serious adverse events (SAEs) per **Section 11.2.4.** below, will be recorded on the AE/SAE case report form (CRF) as appropriate.

Any symptom or event that occurs more than two hours after study dosing will be recorded as an AE on the AE CRF but will not be identified as a dosing reaction.

For this study, an AE will include any untoward or unfavorable medical occurrence associated with:

Study therapy regimens:

Dupilumab/Placebo for Dupilumab
In-clinic OIT dosing
Home OIT Dosing

For the study-mandated procedures below, only the signs and symptoms listed under each procedure will be considered outside normal range and will be recorded as an AE. For all other study-mandated procedures, all AEs will be recorded.

Skin Prick Test

The following events related to SPT will be considered AEs if they occur within 48 hours of the SPT:

- Prolonged (>24 hours) pruritus at the SPT site
- Induration/swelling at the SPT site larger than 10 mm in diameter and lasting more than 24 hours
- Allergic or anaphylactic reaction that requires the use of rescue medications, detailed in **Section 7.2**

Blood Draw

The following events related to a blood draw procedure will be considered AEs:

- Syncope/vasovagal events within 30 minutes of the procedure
- Bleeding from the puncture site lasting more than 30 minutes
- Bruising at the puncture site >5 cm in diameter within 24 hours of procedure
- Erythema at the puncture site >5 cm in diameter within 24 hours of procedure
- Allergic reaction to local skin anesthetic that requires rescue medications
- Infection at the puncture site

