The immune system in the gut actively induces an immune tolerant state to the proteins that are normally consumed. Food allergy occurs when the body has a break in this tolerance, which results in an abnormal immune reaction to food. Milk allergy is an IgE-mediated hypersensitivity reaction following the ingestion of normally innocuous milk protein. Cross-linking of milk-specific IgE (sIgE) bound to high affinity IgE receptors on mast cells and basophils triggers immediate degranulation, and the subsequent release of a diverse array of inflammatory mediators results in severe allergic symptoms such as hives, wheezing, vomiting and, in severe cases, anaphylactic shock. Release of these mediators also initiates type 2 helper T-cell (Th2) cytokine release, which results in eosinophil infiltration and creates a vicious cycle of chronic allergic inflammation. Like other forms of allergy immunotherapy, OIT to milk involves a slow up-dosing of exposure to allergen over time to desensitize or increase the threshold of reactivity to milk. Once reaching a target level of milk protein, subjects are continued on a maintenance dose of milk protein to maintain desensitization. Although many subjects on a maintenance dose of milk protein have demonstrated desensitization to milk (i.e. the ability to tolerate a level of exposure to milk without an allergic reaction), up to 95% subjects exhibit related adverse events (AEs) during OIT with 40% experiencing gastrointestinal (GI) symptoms ([Vázquez-Ortiz 2013](#), [Martorell Calatayud 2014](#), [Mori 2017](#), [De Schryver 2019](#)). While the majority of these are mild and decline with prolonged treatment, approximately 25% of patients experience more severe, unpredictable reactions. Roughly 20 to 30% of patients are unable to complete their up-dosing regimen due to side effects, of which the majority are related to the GI system. In those who do successfully desensitize, an additional issue with current OIT arises, specifically its limited ability to induce clinical tolerance (i.e. the persistence of desensitization after subjects are taken off of OIT) ([Keet 2012](#), [Suárez-Fariñas 2019](#)). In many of the studies with milk OIT, despite years of

immunotherapy, subjects lose their tolerance within weeks of halting daily milk intake, with only 50% or fewer patients maintaining a sustained unresponsiveness after 2 months off OIT.

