1.2. Rationale

1.2.1. Rationale for Investigational Study

This study will investigate whether addition of dupilumab, a fully human monoclonal antibody directed against IL-4R α , will improve OIT in subjects with milk allergy. This study will seek to demonstrate that addition of dupilumab to milk protein OIT will enhance the safety, tolerability, and efficacy of OIT. This will be determined by assessing whether treatment with dupilumab provides an enhanced ability to tolerate a higher cumulative dose

of milk protein during a food challenge after 18 weeks of treatment compared to placebo when given concomitantly with milk protein OIT and whether treatment with dupilumab allows for more rapid up-dosing of milk during desensitization. The differences in safety and tolerability will be assessed through an evaluation of treatment differences in AEs and study drop-out rates.

OIT has demonstrated efficacy in desensitizing food allergic subjects through the promotion of physiologic changes that result in the suppression of an allergic response to the ingested food antigen (Pajno 2018). Desensitization is defined as the ability to tolerate a higher threshold of food allergen without an allergic reaction, while consuming the food regularly. Successful desensitization has been demonstrated in the majority of patients undergoing milk OIT, with rates of success varying depending on the specific definition of desensitization (i.e. milligrams of protein tolerated) and OIT protocol used.

The first randomized, controlled trial of milk OIT, which including treatment with egg, suggested significantly higher rates of desensitization in those receiving OIT compared to a control group (64% vs. 35%, respectively) (Staden 2007). In the first randomized, placebo-controlled study of milk OIT, patients receiving OIT saw an increase in median OFC threshold from 40 mg to 5140 mg after 13 weeks of treatment with 500 mg milk protein, with 36% of those receiving OIT maintaining their tolerance two months after treatment cessation (Skripak 2008). The milk protein dose was escalated to a median of 7000 mg in an open-label follow-up, resulting in 46% of patients tolerating an OFC of 16,000 mg (Narisety 2009). Recent work by Mori et al. mirrored these positive results, with 73% of children in their cohort reaching complete or partial desensitization (Mori 2017).

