2. STUDY HYPOTHESIS/OBJECTIVES

2.1. Hypothesis

We hypothesize that treatment with the IL-4 receptor alpha-chain-targeting antibody, dupilumab, will increase the likelihood of desensitization over the course of 18 weeks and decrease the rate and severity of adverse events associated with cow's milk OIT.

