2.3. Secondary Objectives

Clinical

- To assess the effect of dupilumab (compared to placebo) on tolerance of cumulative doses of ≥ 1040 mg and 4040 mg milk protein at week 18 DBPCFC
- To assess the effect of dupilumab (compared to placebo) on tolerance of cumulative doses of ≥ 1040 mg, ≥ 2040 mg, and 4040 mg milk protein at week 24 DBPCFC
- To compare levels of desensitization, defined as an increase in the cumulative tolerated protein dose (log transformed) of milk protein, from baseline to week 18 and baseline to week 24 DBPCFCs across treatment cohorts

Safety

- To compare the rates and severity of OIT-induced gastrointestinal symptoms in subjects receiving dupilumab compared to placebo.
- To compare the safety of each treatment cohort as measured by rate and severity of allergic and non-allergic AEs during respective study phases
- To compare rates of study completion among treatment cohorts

Exploratory and Mechanistic

[figure not shown]
- To explore the relationship between OIT-induced gastrointestinal symptoms and esophageal eosinophilia in subjects receiving dupilumab compared to placebo, if data is available
- To evaluate the immunological responses associated with OIT-induced AEs and successful desensitization

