5.3. Risk-Benefit of Milk Protein OIT

Based on previously published studies, up to 95% subjects exhibit dose-related AEs during milk OIT, the majority of reactions presenting as mild and declining throughout dose escalation ([Vázquez-Ortiz 2013](#), [Martorell Calatayud 2014](#), [Mori 2017](#), [De Schryver 2019](#)). Approximately 25% of patients experience more severe reactions. Allergic symptoms may include sneezing, rhinorrhea, urticaria, angioedema, flushing, flares of eczema, ocular, nasal, oral and/or throat pruritus, nausea, vomiting, abdominal discomfort, stridor/laryngeal edema, cough, wheezing and/or shortness of breath, in addition to severe anaphylaxis.

The only major atypical AE reported in the literature related to OIT has been several reported cases of EoE ([Hill 2017](#), [Lucendo 2014](#), [Morais Silva 2014](#)). In adult patients with EoE, treatment with dupilumab has shown clinical improvement of symptoms and histology in phase II studies ([Sastre 2018](#)).

Oral food challenges may induce a severe life threatening allergic reaction; however, the risk can be greatly mitigated by conducting the challenges in a highly monitored setting and by initiating the challenge with a very small amount of the food, gradually increasing the dose, and stopping the challenge at the first sign of a reaction. If subjects develop an allergic reaction during the challenges, they may need oral, IM, or IV medications. Additionally, IV catheters may be placed, at clinician discretion for any visit, based on factors such as previous reactions, recent clinical history, and clinical status observed at the visit. Trained personnel, including a study clinician, as well as medications and equipment, will be immediately available to treat any reaction. The anticipated rate of life threatening anaphylactic reactions is <0.1%. There may be a risk that during the study subjects may decrease their vigilance against accidental food allergen ingestion because they believe they are protected from it. Therefore, subjects will be warned that they should continue to practice their usual vigilance against accidental ingestion of food allergens or food allergen-containing foods and reminded to carry their epinephrine auto-injector at all times.

The potential benefit of milk OIT to desensitize milk allergic subjects is outlined in **Section 1.2.1**.

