11.2.3. Unexpected Adverse Event

An "Unexpected AE" or "Unexpected SAR" means an AE or SAR which is considered "unexpected" because it is not listed in the Investigator's Brochure, package insert, or protocol; is not listed at the specificity or severity that has been observed; or is not consistent with the risk information described in the Investigator's Brochure, package insert, protocol, or elsewhere in the current application. Unexpected AEs or Unexpected SARs are further defined in 21 CFR 312.32.

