13.6. Safety Analysis

13.6.1. Adverse Events

Definitions

For safety variables, 2 observation periods are defined:

- The pretreatment period is defined as the time from signing the ICF to before the first dose of study drug.
- The treatment period is defined as the day from first dose of study drug to the end of the study.

Treatment-emergent adverse events are defined as those that are not present at baseline or represent the exacerbation of a pre-existing condition during the on-treatment period.

Analysis

All AEs reported in this study will be coded using the currently available version of the CTCAE. Coding will be to lowest level terms. The verbatim text, the preferred term (PT), and the primary system organ class (SOC) will be listed.

Summaries of all AEs by treatment group will include:

- The number and percentage of subjects with at least 1 AE by SOC and PT
- AEs by severity, presented by SOC and PT
- AEs by relationship to treatment (related, not related), presented by SOC and PT
- Treatment-emergent AESIs (defined with a PT or a prespecified grouping)

Deaths and other SAEs, as well as AEs leading to permanent treatment discontinuation, will be listed and summarized by treatment group.

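### Read by its specific rule, section 11.2.1 takes expected, non-serious immediate OIT reactions out of the AE count that the safety comparison uses, and no other section brings them back by name

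*Combined protocol and SAP*

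**What the plan says.** **The recording rule.** Section 11.2.1 covers symptoms within two hours that are expected under the reference documents. Those "related to administration of study drug or oral food challenge will be recorded as a dosing reaction, not an AE". Home-dosing episodes go on the AE/SAE form if they are Grade 3 or higher or are SAEs. Anything later than two hours after dosing is an AE and not a dosing reaction. Section 11.2.3 sets the limit of expectedness: an event becomes unexpected if, among other things, it "is not listed at the specificity or severity that has been observed".

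**The safety comparison.**
- Section 2.1 hypothesises that dupilumab will "decrease the rate and severity of adverse events associated with" milk OIT.
- Section 2.3 has the objective "To compare the safety of each treatment cohort as measured by rate and severity of allergic and non-allergic AEs during respective study phases".
- Section 1.2.1 says: "The differences in safety and tolerability will be assessed through an evaluation of treatment differences in AEs and study drop-out rates".
- Section 13.6.1 introduces its list with "Summaries of all AEs by treatment group will include". The list covers AEs, treatment-emergent AESIs, deaths, SAEs and AEs leading to discontinuation. It has no dosing-reaction summary.

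**The expected burden.** Section 5.3 states that "up to 95% subjects exhibit dose-related AEs during milk OIT, the majority of reactions presenting as mild". Section 1.1 gives "up to 95% subjects exhibit related adverse events (AEs) during OIT with 40% experiencing gastrointestinal (GI) symptoms".

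**The concern.** The hypothesis and the AE definition use the same word for different sets of events. The background sections call the ordinary immediate reactions to milk OIT adverse events, and the study aims to reduce them. Section 11.2.1 then takes the expected, non-serious ones out of the AE category. If the tables in 13.6.1 are built from AE records alone, they show mainly late, unexpected, serious or severe home events. They could then miss or understate a between-arm difference in the reactions of most interest.

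The two-hour window is also where the protocol itself looks for reactions. Section 5.6 requires at least two hours of observation after each in-clinic increase, and section 5.6.1 asks participants to stay awake for two hours after home doses.

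**Working it through.** No figure in the plan is at issue, so the check sets the sections side by side.

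**Step 1: where each type of OIT reaction goes under the specific rule in 11.2.1.**
- More than two hours after dosing: AE.
- Within two hours, unexpected: AE.
- Within two hours, expected, home dose, Grade 3 or higher or an SAE: AE/SAE form.
- Within two hours, expected, home dose, Grade 1-2, non-serious: dosing reaction, not an AE.
- Within two hours, expected, in clinic, non-serious: dosing reaction, not an AE. The grade exception names home dosing only, so this holds at any grade that still counts as expected under 11.2.3.

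One route back applies to the last two groups. AESIs (11.2.5) must be reported regardless of expectedness (11.5), and 13.6.1 summarises them. For milk OIT these are life-threatening anaphylaxis and GI events that cause prolonged disruption of dosing, so ordinary mild reactions do not qualify.

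**Step 2: what the analysis reads.** Sections 2.1, 2.3 and 13.6.1 refer to AEs, and 1.2.1 to AEs and drop-out. Dosing symptoms are collected (5.5, and the home diary in 6.3), but no section assigns them to a between-arm comparison. Generic text could cover them. The synopsis names allergic reactions beside treatment-emergent AEs, 13.3.2 covers all clinical safety variables, 13.4 summarises all data by arm, and 13.5.2 treats all secondary endpoints descriptively. None of these names dosing reactions.

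**Step 3: text that points the other way.**
- A later sentence in 11.2.1 counts untoward occurrences associated with in-clinic and home OIT dosing as AEs.
- Section 11.3.1 sends events of Grade 1 or higher to the AE form.
- Sections 1.2.3.1, 3.1, 6.4 and 8.3, and footnote 11 of Table 4, use the term AE for symptoms during dosing or challenge.

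The dosing-reaction rule is the more specific instruction, but a site could reasonably follow the others.

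**Step 4: how large it could be.** The share of participants affected is not in the documents. Their background rates give only a rough ceiling for a placebo-plus-OIT arm of 58:
- Any dose-related event: 0.95 × 58 = 55.1.
- GI symptoms: 0.40 × 58 = 23.2 if the base is all subjects, or 0.40 × 0.95 × 58 = 22.0 if it is those with events.

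Assume that 25%, 50% or 75% of these participants have only reactions that the rule records as dosing reactions. An AE-only table would then leave out:
- Any event: 0.25, 0.50 or 0.75 × 55.1 = 13.8, 27.6 or 41.3 participants.
- GI events: 5.5-5.8, 11.0-11.6 or 16.5-17.4 participants.

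The shares are assumptions, and the AE definitions behind the 95% and 40% are not in the documents. These counts illustrate scale and do not estimate an effect on the treatment comparison.

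**The case against.** The strongest reply is that the protocol does not really mean to exclude these reactions. It often uses AE for immediate dosing symptoms, and the later sentence in 11.2.1 and the Grade 1 sentence in 11.3.1 would put them on the AE form. This stands in part. A reader might infer that the omission is certain, and the documents do not support that. It is what the more specific rule produces, in a text that is not consistent.

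A second reply is that GI reactions have their own endpoints in 3.5.2, worded as OIT-induced symptoms rather than AEs, and the diary asks about stomach pain, nausea and vomiting. This also stands. A reader might infer that the GI comparison is lost, but a GI symptom recorded as a dosing reaction can still count there. What remains is that section 13 names no data source for those endpoints, and immediate skin and respiratory reactions have no endpoint of their own. The *safety events* in 3.5.2 might cover them, but the term is undefined.

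Third, safety is also judged on drop-out and study completion, and AESIs are reported whatever their expectedness. These measures are unaffected, but they do not describe the ordinary reaction burden.

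Fourth, the safety analysis is descriptive, the list in 13.6.1 is not stated to be exhaustive, and a final SAP is to follow. A reader might infer a calculable loss of power. The documents plan no formal safety test and give neither the dupilumab reaction rate nor the share of reactions affected, so no such figure can be supported. That the SAP is still open is a reason to settle the point now.

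**Conclusion.** The point holds in a limited form. Under the specific rule in 11.2.1, expected, related, non-serious reactions within two hours are not AEs. For home doses this means Grade 1-2. In clinic it means any grade that still counts as expected and is not reported as an AESI. The descriptive AE comparison then omits much of the immediate reaction burden that the study sets out to reduce. Because other sentences conflict with the rule, inconsistent recording between sites is a further risk.

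This conclusion rests on reading the specific rule as governing and on the tables being built from AE records. The size is unknown, and the 25-75% range above is an assumption. A reader might infer harm to the efficacy result, but the primary endpoint comes from the week 18 food challenge and does not use AE records. Nor are data lost, since the symptoms are captured. It should be fixed before the SAP is final.

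Whether a non-serious in-clinic Grade 3 dosing reaction counts under the severe-adverse-event trigger in 10.3 is a separate point. Sections 10.3 and 11.2.1 should be reconciled on it.

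**What to change.** 1. Reconcile 11.2.1 with 11.3.1 so that it is clear which form records a dosing reaction, and apply this at all sites.
2. In 13.6, add a by-arm summary that pools OIT dosing reactions and AEs: participants with any event and with any GI event, by maximum grade. Keep the AE-only tables as a subset. Report food-challenge reactions separately, because they determine the efficacy outcome.
3. State that the GI-symptom endpoints and the *safety events* endpoint in 3.5.2 draw on both dosing-reaction and AE records, and define *safety events*.

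The cost is a few extra tables and a small wording change to the protocol and SAP. No new data collection is needed, because dosing symptoms and home diaries are already planned (5.5, 6.3).

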11.2.2. Suspected Adverse Reaction

Any AE for which there is a reasonable possibility that the investigational drug (dupilumab, and/or milk OIT) caused the AE. For the purposes of safety reporting, 'reasonable possibility' means there is evidence to suggest a causal relationship between the drug and the AE. A suspected adverse reaction (SAR) implies a lesser degree of certainty about causality than an AE, which means any AE caused by a drug (21 CFR 312.32(a)).

11.2.3. Unexpected Adverse Event

An "Unexpected AE" or "Unexpected SAR" means an AE or SAR which is considered "unexpected" because it is not listed in the Investigator's Brochure, package insert, or protocol; is not listed at the specificity or severity that has been observed; or is not consistent with the risk information described in the Investigator's Brochure, package insert, protocol, or elsewhere in the current application. Unexpected AEs or Unexpected SARs are further defined in 21 CFR 312.32.

